18.2 Regulatory compliance

The trial will not commence until a Clinical Trial Authorisation (CTA) is obtained from the MHRA. The protocol and trial conduct will comply with the Medicines for Human Use (Clinical Trials) Regulations 2004 and any relevant amendments.

Development Safety Update Reports (DSURs) will be submitted to the MHRA in accordance with national requirements. It is the Chief Investigator's responsibility to produce the annual reports as required.

18.3 Health Research Authority (HRA)

HRA approval is required for all UK trials before commencement.

18.4 Protocol amendments

Protocol amendments must be reviewed, and agreement received from the Sponsor for all proposed amendments before submission to the HRA, REC and/or MHRA. Substantial and significant protocol amendments will also be reviewed by the NIHR before submission. The only circumstance in which an amendment may be initiated before HRA, REC and/or MHRA approval is where the change is necessary to eliminate apparent, immediate risks to the participants (Urgent Safety Measures). In this case, the accrual of new participants will be halted until the HRA, REC and/or MHRA approval has been obtained.

18.5 Peer review

The trial proposal has been through the NIHR peer review process as a requirement of the HTA award. It has also been discussed and widely accepted by the Academic Committee of the Society of British Neurological Surgeons, the Age and Ageing National Specialty Group of the NIHR CCRN and the British Neurosurgical Trainee Research Collaborative. The support of the UK Neurosurgical Research Network will allow us to roll out the substantive trial across the NHS.

18.6 Declaration of Helsinki and Good Clinical Practice

The trial will be performed in accordance with the spirit and the letter of the Declaration of Helsinki, the conditions and principles of Good Clinical Practice, the protocol and applicable local regulatory requirements and laws.

18.7 Good Clinical Practice (GCP) Training

All trial staff must hold evidence of appropriate GCP training or undergo GCP training before undertaking any responsibilities on this trial. This training should be updated every 3 years or in accordance with your Trust's policy.

19. Sponsorship, Financial and Insurance

The trial is sponsored by Cambridge University Hospitals NHS Foundation Trust and the University of Cambridge.

Cambridge University Hospitals NHS Foundation Trust, as a member of the NHS Clinical Negligence Scheme for Trusts, will accept full financial liability for harm caused to participants in the clinical trial caused through the negligence of its employees and honorary contract holders. There are no specific arrangements for compensation should a participant be harmed through participation in the trial, but no one has acted negligently.

The University of Cambridge will arrange insurance for negligent harm caused due to protocol design and for non-negligent harm arising through participation in the clinical trial.

This trial is funded by the National Institute for Health Research (NIHR) HTA Programme Grant (NIHR152722). The views expressed are those of the authors and not necessarily those of the NIHR or the Department of Health and Social Care.

20. Monitoring, Audit and Inspection

The investigator must make all trial documentation and related records available should an MHRA Inspection occur. Should a monitoring visit or audit be requested, the investigator must make the trial documentation and source data available to the Sponsor's representative. All participant data must be handled and treated confidentially. The Sponsor's monitoring frequency will be determined by an initial risk assessment performed before the start of the trial. A detailed monitoring plan will be generated detailing the frequency and scope of the monitoring for the trial. Throughout the course of the trial, the risk assessment will be reviewed, and the monitoring frequency adjusted as necessary.

Monitoring of participating sites should occur in line with the trial specific monitoring. Remote monitoring will be conducted for all participating sites. The scope and frequency of the monitoring will be determined by the risk assessment and detailed in the Monitoring Plan for the trial.

21. Publication policy

Ownership of the data arising from this trial resides with the coordinating trial team. On completion of the trial, the data will be analysed and tabulated, and a Final Trial Report (FTR) will be prepared. We intend to disseminate the findings of the TOP-TBI trial via high-impact factor journals, the HTA journal and presentations at national and international meetings. We will target conferences organised for the different health professionals who care for patients with TBI, including those in neurosurgery, intensive care medicine, neurology, rehabilitation medicine, and emergency medicine. Research findings will be disseminated to relevant service user groups and charities (Thrombosis UK and Headway) through newsletters, website posts and public presentations. The TOP-TBI study website will also include dedicated pages for members of the public. We propose to hold open days in some of the hospital departments participating in the study where members of the public will be invited to find out about the study.

22. Archiving

As per current regulation, once the trial has come to an end and the analysis has been reported to the regulatory authorities, essential trial documentation as part of the TMF will be archived in keeping with the Sponsor's policy and applicable regulations for a period of 5 years

All trial-related documentation and data as part of the investigator site file (including the site-level pharmacy file) will be archived following the participating site's standard operating procedures and the Sponsor's timelines. These procedures state suitable locations to be specified at the time of archiving with limited access to named members of the research team only.

23. References

- 4.** Surgical site bleeding that requires a second intervention open, arthroscopic, endovascular or a hemarthrosis of sufficient size as to interfere with rehabilitation by delaying mobilization or delayed wound healing, resulting in prolonged hospitalization or a deep wound infection, and/or
- 5.** Surgical site bleeding that is unexpected and prolonged and/or sufficiently large to cause hemodynamic instability, as assessed by the surgeon. There should be an associate fall in haemoglobin level of at least 20 g L^{-1} (1.24 mmol L^{-1}), or transfusion, indicated by the bleeding, of at least two units of whole blood or red cells, with temporal association within 24 h to the bleeding.
- 6.** The period for collection of these data is from start of surgery until five half-lives after the last dose of the drug with the longest half-life and with the longest treatment period (in case of unequal active treatment durations).
- 7.** The population is those who have received at least one dose of the study drug.

Reference: Shulman S, Angera U, Bergqvist D, Eriksson B, Lassen M.R, Fisher W. N. Definition of major bleeding in clinical investigations of antihemostatic medicinal products in surgical patients – On behalf of the subcommittee on control of anticoagulation of the scientific and standardisation committee of the International Society on Thrombosis and Haemostasis. *Journal of Thrombosis and Haemostasis*, 8: 202–204, DOI: 10.1111/j.1538-7836.2009.03678.x

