8.6.2 Secondary outcome measures

- Proximal DVT at asymptomatic screening ultrasound (*only relevant for sites where they undertake screening ultrasound as part of routine clinical practice*)
- Progression of intracranial haemorrhage within 14 days after randomisation requiring neurosurgical intervention
- Progression of intracranial haemorrhage on routinely performed imaging
- Adverse events, of special interest (AESI) including major and clinically relevant bleeding events (bleeding events are assessed and reported in accordance with criteria published by the International Society of Thrombosis and Haemostasis) (see Appendix 1)
- VTE at 90 days
- 7-day, 30-day, and 12-month mortality
- Glasgow Outcome Scale-Extended (GOS-E) at 6 and 12 months

- Quality of life (EQ5D-5L) at Day 30 or discharge, 6 and 12 months
- Length of stay of index admission
- Economic analysis (see section 16.5)

Given patients with TBI are prone to VTE events, some hospital practices undertake a screening ultrasound to investigate for asymptomatic DVTs. Sites will be allowed to perform screening ultrasound at their discretion; however, this trial will only include **asymptomatic proximal DVT** diagnosed by ultrasound. A proximal DVT is defined as a DVT that is in the popliteal, femoral or iliac veins. A DVT that is located below the knee and is confined to the calf veins (peroneal, posterior, anterior tibial, and muscular veins) without a proximal component will not be recorded. This is because up to 25% of patients admitted to an intensive care environment can have asymptomatic distal DVTs that are of no clinical relevance.

The trial will allow any **asymptomatic proximal DVT** as part of asymptomatic screening ultrasound diagnosed from the day of randomisation up until day 29 post randomisation. This will be recorded as a secondary outcome.

9. Selection and withdrawal of participants

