11.5.2 Assessments at time point

- Adverse events of special interest (AESI) during treatment and follow up timepoints up to 12 months. including major and clinically relevant bleeding events
- Asymptomatic DVT assessment with an ultrasound scan during hospital stay (*only relevant for all sites that perform screening ultrasound as part of routine clinical practice*)
- Assessment for VTE during hospital admission, 30 days and 90 days
- Progression of intracranial haemorrhage on routinely performed imaging within 14 days after randomisation requiring neurosurgical intervention
- Quality of life (EQ5D-5L) at Day 30 or discharge, 6 and 12 months
- Mortality at 7-days, 30 days and 12 months
- Glasgow Outcome Scale-Extended (GOS-E) at 6 and 12 months
- Length of stay of index admission
- Economic analysis at 12 months

Method of follow-up

Prospective follow-up data (at 30 days - primary endpoint), 90 days, 6- and 12-months post-enrolment) will be collected electronically via email or online formats such as Qualtrics or MS Forms or via postal questionnaires or telephone interviews by blinded study personnel if participants cannot complete forms electronically/return postal questionnaires. The questionnaires will include questions on any longer-term effects of VTE, the extended Glasgow Outcome Scale (GOSE, only 6 and 12 month FU) and EQ-5D-5L questionnaire (30 days, 6- and 12-month FU). Re-admission and out-patient data will be captured from Hospital Episode Statistics (HES) data.

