12.1 Definitions

12.1.1 Adverse event (AE)

Any untoward medical occurrence in a participant or clinical trial participant administered a medicinal product which does not necessarily have a causal relationship with this treatment. An adverse event can therefore be any unfavourable and unintended sign (including an abnormal laboratory finding), symptom, or disease temporally associated with using an investigational medicinal product, whether considered related to the investigational medicinal product.

Recording of adverse events must start from the point of Informed Consent regardless of whether a participant has yet received a medicinal product.

The safety profiles of all drugs used for VTE prophylaxis are well established, and due to the pathology of TBI, trial participants will be regularly monitored and assessed in the intensive care environment at regular intervals throughout the trial, over and above routine clinical care. Given the pragmatic nature of the trial and that the potential risk associated with the trial drug is 'no higher than standard care',

only AEs of special interest (AESI) will be recorded on CRF and sent to the coordination centre as listed below.

Adverse events of special interest (AESI) – assessed and reported in accordance with criteria published by the International Society of Thrombosis and Haemostasis. – see Appendix 1.

The following should all be recorded on the AESI form in the eCRF.

- Thrombocytopenia
- Thrombocytosis
- Prosthetic cardiac valve thrombosis
- Cutaneous vasculitis
- Eosinophilia
- Skin reactions
- Angioedema
- Priapism
- Stevens-Johnson syndrome
- Acute generalised exanthematous pustulosis (AGEP)

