12.4 Evaluation of AESI; SAR / SUSAR

The Sponsor expects that adverse events are recorded from the point of Informed Consent regardless of whether a participant has yet received a medicinal product. The investigator should evaluate individual adverse events. This includes the evaluation of its seriousness and any relationship between the investigational medicinal product(s) and/or concomitant therapy and the adverse event (causality).

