12.4.4 Recording of adverse events and Adverse Events of Special Interest

Selected AEs and ARs will be recorded and reported as part of the trial. Adverse events and adverse reactions should be recorded in the patient's medical notes as part of their routine care, as determined by their treating clinician.

Adverse Events of Special Interest (AESIs) will be recorded in the trial as part of secondary outcome data collection in the AESI eCRF. AESI that will be collected in the trial include those below:

- Thrombocytopenia
- Thrombocytosis
- Prosthetic cardiac valve thrombosis
- Cutaneous vasculitis
- Eosinophilia
- Skin reactions
- Angioedema
- Priapism
- Stevens-Johnson syndrome
- Acute generalised exanthematous pustulosis (AGEP)

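### Appendix 1 limits the bleeding outcome to dosed patients from the start of surgery, which contradicts the body of the protocol and does not fit a late arm that may never be dosed; the objective to compare every SAE cannot be met either

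*Protocol*

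**What the plan says.** **Bleeding.** Section 8.6.2 makes bleeding a secondary outcome and points to the appendix: "bleeding events are assessed and reported in accordance with criteria published by the International Society of Thrombosis and Haemostasis) (see Appendix 1". Appendix 1 then gives more than event definitions. Item 6 sets a period: "The period for collection of these data is from start of surgery until five half-lives after the last dose". Item 7 sets a population: "The population is those who have received at least one dose of the study drug". The source cited beneath is titled "Definition of major bleeding in clinical investigations of antihemostatic medicinal products in surgical patients".

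The body of the protocol says otherwise:

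- Section 11.5.2 lists "Adverse events of special interest (AESI) during treatment and follow up timepoints up to 12 months. including major and clinically relevant bleeding events".
- Section 12.1.1: "Recording of adverse events must start from the point of Informed Consent regardless of whether a participant has yet received a medicinal product". Section 12.4 repeats that "adverse events are recorded from the point of Informed Consent regardless of whether a participant has yet received a medicinal product".
- Section 9.1 admits patients on acute traumatic CT changes; surgery is not required.
- Sections 9.3.2 and 9.3.4 withhold prophylaxis in the late arm for 120 hours and then leave it to clinical discretion, including never giving it.

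The AESI lists in 12.1.1 and 12.4.4 (the latter introduced by "AESI that will be collected in the trial include those below") name ten conditions. Bleeding is not among them.

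**Serious adverse events.** Section 8.5.2 sets an objective to compare every serious adverse event between arms. Section 12.5 states that SAEs are not recorded or reported in the trial, apart from those that are AESI. Section 12.1.9 adds that expected complications of TBI are not recorded as SAEs.

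**The concern.** Bleeding is the natural counterweight to any VTE benefit from earlier anticoagulant prophylaxis after intracranial injury. A population defined by having received a dose is close to the whole of the early arm but only a clinician-selected part of the late arm. That selection happens after randomisation, differs between arms by design, and can depend on prognosis or on bleeding itself. Section 6.3 reports that patients with major extracranial injury were more likely to receive prophylaxis. A late-arm patient who bleeds before 120 hours may never be dosed, and would then leave the comparison.

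The period in item 6 is also undefined for many participants: it has no start without surgery and no end without a last dose. Sites and analysts cannot tell which rule governs.

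On SAEs, the objective promises a comparison for which most of the data will not exist.

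**Working it through.** **1. The two sets of rules side by side**

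| | Appendix 1, items 6-7 | Body of protocol |
|---|---|---|
| Who | At least one dose | Dosed or not (12.1.1, 12.4) |
| Start | Start of surgery | Informed consent (12.1.1, 12.4) |
| End | Five half-lives after last dose | Up to 12 months (11.5.2) |

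They differ on all three points. The intention-to-treat statement in 15.1 covers the principal analysis and does not expressly override item 7 for bleeding.

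**2. Denominators.** Enrolment is 1512 (8.3, 15.3). The protocol's 1164 for 10% versus 5% reproduces exactly with the pooled two-proportion formula (two-sided 5%, 90% power, 1:1). The allocation ratio is not stated; at 1:1 there are 1512/2 = 756 per arm. Let *u* be the share of the late arm never dosed. The protocol does not forecast it; 9.3.2 gives 50% without prophylaxis in routine care, used here as an assumption. Excluded = 756*u*: 227, 378 and 529 for *u* = 0.3, 0.5 and 0.7. At *u* = 0.5 the comparison is 756 versus 378.

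**3. Power.** The protocol gives no bleeding rate and claims no power for bleeding, so the rates are illustrative.

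Power = Φ{[|p₁−p₂| − 1.96√(p̄(1−p̄)(1/n₁+1/n₂))] / √(p₁(1−p₁)/n₁ + p₂(1−p₂)/n₂)}, with p̄ the pooled proportion.

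For 6% early versus 3% late:

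- 756 versus 756: (0.03 − 0.0209)/0.01064 = 0.856, so power is 0.80.
- 756 versus 378: (0.03 − 0.0269)/0.01231 = 0.251, so power is 0.60.

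| Early vs late | All randomised | u = 0.3 | u = 0.5 | u = 0.7 |
|---|---|---|---|---|
| 4% vs 2% | 0.63 | 0.52 | 0.42 | 0.26 |
| 6% vs 3% | 0.80 | 0.71 | 0.60 | 0.41 |
| 10% vs 5% | 0.96 | 0.92 | 0.85 | 0.67 |

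**4. Direction of bias.** Assume a true risk *b* = 4% in both arms, *u* = 0.5 and the whole early arm dosed. Let *rr* be the bleeding risk of late-arm patients who would be dosed relative to those who would not, and *f* the share of bleeds before 120 hours, with those patients then not dosed.

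r₁ = *rr*·*b*/(0.5*rr* + 0.5); apparent late risk = r₁(1−f)/(1−r₁f).

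Example, *rr* = 1 and *f* = 0.3: 0.04 × 0.7/(1 − 0.012) = 2.83%. False-positive chances come from 400,000 simulated trials:

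| Scenario | Late arm reads | False excess, early | False excess, late |
|---|---|---|---|
| All randomised | 4.0% | 0.025 | 0.025 |
| (a) rr = 1, f = 0.3 | 2.8% | 0.15 | 0.002 |
| (a) rr = 1, f = 0.5 | 2.0% | 0.40 | <0.001 |
| (b) rr = 2, f = 0 | 5.3% | 0.002 | 0.18 |
| (c) rr = 2, f = 0.3 | 3.8% | 0.03 | 0.02 |

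**5. Undefined start.** The surgery rate is not given. If 20% to 50% of patients had surgery, 1512 × 0.8 = 1210 down to 1512 × 0.5 = 756 would have no start date under item 6.

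**6. SAEs.** What 12.5 and the outcome list make available in both arms is SAEs that are AESI, together with all-cause deaths. Other SAEs stay in the medical notes, and serious adverse reactions are reported only during trial treatment. The full set named in 8.5.2 is therefore not available.

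**The case against.** The best reply is that items 6-7 look like wording carried over from a surgical definition, and that the body of the protocol points to collection in everyone: recording from consent, bleeding to 12 months, AESI assessment at every time point in Table 2. On that reading the result is ambiguity rather than lost data, and an analysis plan not seen here could set the population. Collection may indeed cover all patients. But 8.6.2 invokes the appendix for reporting as well as assessment, and no analysis plan can recover bleeds from a site that followed item 6.

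Bleeding arguably enters the AESI by reference, because 12.1.1 cites Appendix 1 just before its list and the 12.4.4 list need not be exhaustive. That softens the omission. Yet 12.1.1 tells sites what goes on the AESI form, and bleeding is not there.

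Other harms do not depend on Appendix 1: haemorrhage progression needing neurosurgery, progression on imaging, and mortality. This stands and limits the damage to one secondary outcome.

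The bias figures rest on stacked assumptions, and this also stands. If late-arm patients who bleed early are dosed at half the usual rate rather than never, the 0.15 and 0.40 in scenario (a) fall to about 0.06 and 0.11. If 20% of early-arm bleeds are also lost because prophylaxis is withheld (11.9 allows it), they become about 0.05 and 0.19, while the 0.18 in scenario (b) rises to about 0.41. The figures show that error can go either way; they do not predict its size.

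The SAE point is a separate and smaller mismatch. Selective recording is defensible in a Type A trial; the fault lies in the breadth of the objective.

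**Conclusion.** The concern holds on both parts. Appendix 1 items 6-7 contradict 11.5.2, 12.1.1 and 12.4 on who is counted and for how long, and cannot be applied to patients without surgery or without a dose. Followed as written, they replace a randomised comparison of bleeding with one selected after randomisation. With 1:1 allocation and 30% to 70% of the late arm never dosed, 227 to 529 of 756 late-arm patients would be left out, and power for 6% versus 3% would fall from 0.80 to between 0.71 and 0.41. The direction of bias cannot be known in advance. All rates behind these figures are assumptions; the contradiction in the text is not. The objective in 8.5.2 cannot be met under 12.5 and 12.1.9. The primary outcome is unaffected, so this should be corrected but does not undermine the trial as a whole.

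**What to change.** - **Appendix 1:** keep items 1-5 as event definitions. Replace items 6-7 with a statement that bleeding is collected and compared in all randomised patients, by allocated arm, from randomisation. Name one fixed window for the main comparison, for example to day 30, and keep the 12-month collection in 11.5.2.
- **12.1.1 and 12.4.4:** add bleeding by the ISTH criteria to both AESI lists.
- **8.5.2:** replace the promise to compare every SAE with the harms recorded in both arms: haemorrhage progression, ISTH bleeding, AESI and all-cause death.

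The cost is wording in four places and, if bleeding is not already on it, one entry on the AESI form. No visits are added, since Table 2 already schedules AESI assessment for all participants at every time point.
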